UI CAAN	C ancer S creening; A ccess; A wareness; N avigation
USPSTF	U.S. Preventive Services Task Force

1.0 Project Summary/Abstract

The UI CAAN (Cancer Screening; Access; Awareness; Navigation) Project is a community focused cancer education, prevention, screening and navigation program aimed at addressing the elevated burden of cancer among marginalized communities in the UI Cancer Center (UICC) catchment area. Cook County is populated by some of the most diverse racial/ethnic groups in the US; 2017 census data showed that almost 50% of the Cook County population is Hispanic/Latino (25%) and African American (24%). The top five cancers with the highest incidence rates in the UICC catchment area include Lung, Prostate, Colorectal (CRC), Breast and Cervical cancers. Within the UICC catchment, under-represented racial/ethnic minorities carry the greatest burden of cancer disparities, which is further impacted by social determinants of health. Cancer disparities in racial/ethnic minorities are further impacted by intersecting identities such as being a sexual and gender minority (LGBTQ) or by being differently abled.

UI CAAN advances health equity by addressing barriers to care; mobilizing community assets and partners; coordinating comprehensive prevention; screening and navigating patients to healthcare services and resources; and engaging community members as a vital part of the health care workforce. By employing community health workers and navigators *from* communities that are most impacted by cancer inequities, the UI CAAN addresses community inequities from an asset-based model. Creating a cancer screening/navigation workforce representative of the diversity of the UICC communities also addresses workforce needs of underserved communities. The overall goal of this project is to evaluate the feasibility of conducting community-based colorectal cancer screening in an urban environment. We will study the efficacy of the community-based intervention on improving CRC screening rates. A controlled trial will be conducted to achieve these objectives. Additionally, we will characterize factors that inhibit and/or facilitate colorectal cancer screening among people in the UICC catchment area.

2.0 Background/Scientific Rationale

Population health can be improved by implementing effective screening programs for CRC. CRC is the second-leading cause of cancer death in the United States. The USPSTF recommends screening for CRC starting at age 50 years and continuing until age 75 years. The American Cancer Society (ACS) recommends screening starting at age 45. Fecal immunochemical tests (FITs), which identify intact human hemoglobin in stool, are FDA approved tests for detecting CRC (Lin et al. 2016). Screening strategies that employ annual screening with FIT have been shown to reduce CRC deaths (Lin et al.

2016). A 2015 community health needs assessment in the South Shore area (<http://www.southshorehospital.com/wp-content/uploads/2014/07/Community-Health-Needs-Assessment-2013.pdf>) showed that CRC deaths are an area of opportunity for health improvement in the South Shore community area.

The CRC screening process is complex, particularly for those that screen positive and require diagnostic evaluation, treatment, and/or repeat screening following an abnormal test. Furthermore, screening for CRC is not a one-time activity and instead requires annual screening to be most effective. The UI Cancer Center Community Outreach and Engagement (COE) program is housed within the Office of Community Engaged Research and Implementation Science (OCERIS) of the UI Cancer Center. OCERIS is the community engagement and health disparities research arm of the Community Outreach and Engagement Program of the UI Cancer Center's Cancer Prevention and Control Program (CPC). Established in 2014, OCERIS has led the mission of the UI Cancer Center to ensure the community is at the center of research, screening, prevention, and supporting the training of a diverse and inclusive biomedical and population health workforce. Mission: The mission of OCERIS is to lead the UI Cancer Center in integrating the community in everything it does through fostering community based screening, prevention, education, building community-academic partnerships, to conduct transdisciplinary research, training and education to reduce the burden of cancer health disparities and inequities.

This study is a direct results of OCERIS' involvement in ongoing community based screening and navigation programs, and will go beyond quality improvement in screening to extend to answer the important research questions about engagement within a healthcare system and lack of follow-up.

3.0 Objectives/Aims

We propose to address the multiple determinants of health that impact CRC screening in the South Shore community in the UI Cancer Center's catchment area by conducting a quasi-experimental intervention to test the effectiveness of FIT tests dispensed by community stakeholders (community-dispensed) versus FIT tests dispensed using standard of care procedures by a clinic (clinic-dispensed) on FIT test return rates. This

study will follow ACS guidelines for FIT testing, with the South Shore community area assigned to the intervention group (community-dispensed). CRC screening within the Mile Square Englewood Health Center, using standard of care, will serve as our control group to use for comparison (clinic-dispensed). The intervention will include a multifaceted approach to health education and community engagement focused on CRC led by a team of trusted health champions (community leaders, a barber, a hair salon, and community health workers) in the South Shore community area. We specifically propose to investigate the following three specific aims to be achieved over the three-year project period:

Aim 1: To assess the feasibility and efficacy of the community-based CRC screening intervention in increasing CRC screening rates;

Aim 2: To evaluate individual-level knowledge related to CRC screening and risk factors;

Aim 3: To characterize individual -level facilitators and barriers to engaging in CRC screening and related diagnostic tests and treatment when applicable.

4.1 Eligibility

Community Intervention Group/Arm

Eligibility to participate in this community intervention will primarily be driven by location of residence and age, since screening CRC have established age criteria for screening initiation. A total of four community health navigators will be deployed in the South Shore community area. Each navigator will be trained to understand the eligibility criteria and determine subject eligibility. For those that consent to take the FIT kit and return it, the navigator will document the participants' eligibility in the appropriate REDCap participant information form (attached).

Standard of Care Comparison Group/Control Arm

Within the Mile Square Health Center system, lay navigators already work to do colorectal cancer screening in the Mile Square Health Center setting. It is standard of care for these navigators to engage patients in health education and awareness regarding the need for colorectal cancer screening. As such, each navigator is familiar with eligibility criteria for screening under standard of care. For the purposes of this study, we will use deidentified aggregate data from the CRC screening navigation program at the Mile Square Health Center in Englewood as a comparison group to evaluate the value of the community intervention relative to standard of care. As general practice, each navigator at MSHC keeps a running tally of the number of patients approached, deemed eligible, and who opt to participate in colorectal cancer screening during each day the navigator works in the health center setting.

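### Aim 1 infers efficacy from an unadjusted FIT-return comparison of South Shore with one Englewood clinic, where arm and site coincide, the control counts cannot be adjusted, and sample sufficiency is unsupported

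*Combined protocol and SAP*

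**What the plan says.** **Claim.** Section 1.0 states: "We will study the efficacy of the community-based intervention on improving CRC screening rates". Aim 1 in 3.0 and 9.1, and the primary aim in 12.1, pair feasibility with efficacy. Section 6.2 says that evidence of efficacy would support community-based programmes of this kind as a potential tool.

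**Assignment.** Section 3.0 calls the study quasi-experimental, "with the South Shore community area assigned to the intervention group (community-dispensed)", and takes the Mile Square Englewood clinic as the whole control group. It words the contrast as "FIT tests dispensed by community stakeholders (community-dispensed) versus FIT tests dispensed using standard of care procedures by a clinic (clinic-dispensed)". Section 4.1 words it more broadly: "to evaluate the value of the community intervention relative to standard of care".

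**Control data.** Section 4.1 says "we will use deidentified aggregate data from the CRC screening navigation program at the Mile Square Health Center in Englewood as a comparison group". On who is eligible there, it says that "each navigator is familiar with eligibility criteria for screening under standard of care". Section 4.2 names Englewood users within the study criteria (45 to 74, English-speaking, no CRC screening in 12 months). Table 2 describes the clinic procedures as an existing programme separate from the research. The control count lists in 5.0 and in the first control-arm paragraph of 6.3 give numbers approached, eligible, both taking and returning a kit, and FITs returned. The last paragraph of 6.3 lists persons who receive and persons who return the FIT. None lists age or sex.

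**Analysis.** Section 9.1 compares return rate and average return time at the two sites to see whether they are similar. It names no denominator, interval or adjustment.

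**Sample size.** Section 5.0 targets at least 600 in South Shore. Section 12.1 anticipates that the sample will be sufficient for arm comparisons and gives no inputs.

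**The concern.** A difference in FIT return, or the lack of one, could come from the community programme, from the places, from who is counted at each place, or from how the rate is formed. The plan gives no means of telling these apart, yet section 6.2 would read a favourable difference as evidence of efficacy.

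The parts are not equally curable. Confounding with site is built into a design with one site per arm; it can only be stated. Eligibility, denominator and age and sex mix can be improved, but only through what is asked of the clinic. If the aggregate counts are compiled without that detail, it may not be recoverable later.

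The label of the contrast matters too. A $25 incentive (5.0) and a reminder call at two weeks (6.3) are described only for South Shore. Outside the barber shop and salon the incentive is paid once the FIT arrives, so it is tied directly to the outcome being compared. A difference between arms would not isolate who dispensed the kit.

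**Working it through.** **1. Inputs.** The documents give one number: at least 600 in South Shore (5.0). They give no control N, expected return rate, difference of interest, alpha or power, so the sufficiency statement has no figure to reproduce. Every rate, control N and site difference below is an assumption used to show a range.

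**2. Site.** Expected observed difference = intervention effect + baseline difference in return between the two places. The second term contains no sample size, so any baseline gap passes one-for-one into the contrast. As an illustration, take no intervention effect and a site gap of 5 points (55% v 50%), tested with a two-sided 5% two-proportion z test. At 600 per arm the pooled rate is 0.525 and the standard error is sqrt(0.525 × 0.475 × 2/600) = 0.0288. The test would be significant 41.1% of the time. At 300 controls the figure is 29.4%. More controls make the false reading more likely.

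**3. Precision.** 95% half-width at 50% return in both arms = 1.96 × sqrt[0.25 × (1/600 + 1/n0)]. The difference d detectable with 80% power, starting from 50%, solves d = (1.96 + 0.84) × sqrt[(0.5 + d)(0.5 − d)/600 + 0.25/n0].

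| Control N (n0) | Half-width, points | Detectable difference, points |
|---|---|---|
| 150 | 8.9 | 12.7 |
| 300 | 6.9 | 9.8 |
| 600 | 5.7 | 8.0 |
| 1200 | 4.9 | 7.0 |

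For n0 = 300: 1.96 × sqrt[0.25 × (0.001667 + 0.003333)] = 1.96 × 0.03536 = 0.069. Whether the sample suffices depends on a number that the plan does not state. These figures cover sampling error within each site only.

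**4. Eligibility, denominator and case mix.**
- *Criteria.* Section 4.2 nominally covers Englewood users. The counts, however, come from navigators working to standard-of-care criteria that are not set out (4.1), in a programme described as separate from the research (Table 2). No step checks or restricts the counts.
- *Denominator.* The last paragraph of 6.3 supplies the natural one, persons who receive the FIT. The lists in 5.0 and earlier in 6.3 have no separate count of recipients. Section 9.1 lists FITs distributed and returned but does not define the rate.
- *Strata.* With no age or sex in any control list, no adjustment is possible, even for easily measured differences.

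**5. What standardisation can do.** Hypothetical six-cell example with a true within-cell difference of zero. Ages 45-49/50-64/65-74 are 25/50/25% in South Shore and 10/50/40% in Englewood; men are 50% and 35%. Return by age band is 40/50/60% in men and 45/55/65% in women.
- South Shore crude: 0.50 × 50% + 0.50 × 55% = 52.5%.
- Englewood crude: 0.35 × 53% + 0.65 × 58% = 56.25%.
- Crude difference: −3.75 points. Standardised to the South Shore mix: 0.

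| Control N | Crude half-width | Standardised half-width | Smallest control cell |
|---|---|---|---|
| 150 | 8.9 | 10.2 | about 5 |
| 300 | 6.9 | 7.7 | about 10 |
| 600 | 5.6 | 6.1 | 21 |

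Standardisation removes the measured mix difference for about 0.5 point of half-width at 600 controls. It does nothing about site.

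**The case against.** The best defence is that the plan is open about what it is. Section 3.0 says quasi-experimental, 1.0 gives feasibility as the overall goal, 9.1 asks whether rates and times are similar, and 12.1 says the analyses are meant to inform future interventions. This stands in part: the design is not hidden, and feasibility, Aim 2 and Aim 3 do not depend on the control arm. But the efficacy wording remains in the aims, and 6.2 says what would be concluded from it.

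A second defence is that returned over received is the obvious rate and that 6.3 already provides for it. That is fair. What remains is to name it in 9.1 and bring the other lists into line.

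Several stronger readings are tempting but not supported:
- *The clinic screens from a different age.* Section 2.0 cites two starting ages, 50 from the USPSTF and 45 from the ACS (for the latter, "The American Cancer Society (ACS) recommends screening starting at age 45"), but 3.0 says the study follows ACS guidelines and 4.2 includes Englewood users. The match is unconfirmed; nothing shows that the criteria differ or that the clinic has no patients aged 45-49.
- *The rate might be taken over eligible patients.* No section plans that.
- *Control counts include kits from community events.* Table 2 describes education, referral and screening at those events, not dispensing of kits.
- *Return times will have no SD.* Section 6.3 tracks control return times, and 9.1 commits generally to means and standard deviations. Whether the aggregate data can deliver them is open.
- *Clinic patients get no help.* Table 2 says clinic navigators assist with return; incentives and reminder calls there are simply not mentioned.

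Finally, the daily tally may not support strata, and standardising by age and sex leaves clinic attachment and incentives untouched. Both points stand, and the fix allows for them.

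**Conclusion.** The point holds and should be fixed. Run as written, Aim 1 yields an unadjusted contrast, fully confounded with site, that the plan would call efficacy. That conclusion rests on the text alone.

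The documents do not allow the size of the bias to be estimated: any baseline difference between the sites enters in full. Sampling precision runs from about ±8.9 points with 150 controls to ±4.9 with 1200, assuming 50% return and exactly 600 in South Shore.

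A reader might infer that the sample is too small. The documents do not show that: about 600 controls would detect roughly 8 points on sampling error alone. The statement in 12.1 is unsupported because the control N is missing. Nor does the point make the study invalid; it limits what the arm comparison can be said to show.

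**What to change.** 1. **Clinic data request (5.0 and 6.3).** Bring the count lists into line with the last paragraph of 6.3, so that Englewood supplies persons who received a FIT and persons who returned it. Limit them to the study criteria where the clinic can apply these, and split by age band and sex where available. State any criterion that cannot be applied.
2. **Analysis (9.1).** Define return rate as returned over received. Report the crude difference with a 95% CI and, beside it, an age- and sex-standardised difference over strata present at both sites, collapsing sparse cells. For South Shore, use age and sex recorded for all kit recipients, not the survey that comes back with the FIT, which only returners supply; confirm that the participant information form captures both. If the clinic can supply no strata, report the crude difference and say so. Give a CI for the difference in mean return time if the clinic's data include an SD or individual times.
3. **Claim (12.1, carried through 1.0, 3.0, 6.2 and 9.1).** Replace the sufficiency statement with the precision expected for the control N the clinic can supply, and note that the intervals exclude between-site variation. Describe the result as a quasi-experimental association of the whole community package versus clinic standard of care, not as efficacy.

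**Cost.** No added participants. The price is a more detailed clinic query that the daily tally may only partly support, a slightly wider interval (about 0.5 point at 600 controls in the example, 1.3 at 150, where cells would need collapsing) and a weaker claim.

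As a separate drafting point, 4.2 joins the two location conditions with 'or', while 4.3 and Table 1 list both without saying which arm each applies to; these should be reconciled.

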4.2 Inclusion Criteria

- Male or female adults ages 45 to 74, who speak English and reside in or near the South Shore community area or utilize

the Mile Square Englewood Health Center. Must not have had CRC screening in the previous 12 months.

4.3 Exclusion Criteria

- Adults ages <45 or >74, those that do not speak English, do not reside in or near the South Shore community area, do not utilize the Mile Square Englewood Health Center, or have had CRC screening in the previous 12 months.

Table 1. Inclusion and Exclusion Criteria

Cancer Screening	4.1 Inclusion Criteria	4.2 Exclusion Criteria
Colorectal	Male or Female Age ≥45 and < 75 years Resides in or near the South Shore community area (within UI Health MSHC-South Shore Clinic Service Area) Utilizes the Mile Square Englewood Health Center	Age <45 or >75 years Does not reside in or near the South Shore community area (within UI Health MSHC- South Shore Clinic Service Area) Does not utilize the Mile Square Englewood Health Center Does not speak English Has received CRC screening in past 12 months

5.0 Subject Recruitment and Enrollment

Participants will have an opportunity to enroll in this project at multiple points as summarized in Table 2. We will enroll at least 600 men and women across a three-year period for CRC screening in the South Shore community area, and acquire deidentified aggregate comparison data for the men and women who engage in CRC screening in the Mile Square Englewood Health Center across the same three-year period.

Community Intervention Group/Arm

For the intervention arm, the team of community navigators will recruit participants from multiple venues. We will work with local business owners who are actively engaged in health advocacy and will use their local businesses as sites of participant recruitment (Cut It Out Curt, a barber shop and a hair salon (Location TBD)) to identify and inform eligible community members within or near the South Shore community area about CRC screening. These partners will post the attached CRC screening flyer, and engage with each potential participant to provide information and education about CRC screening using the attached script. If the participant is interested, the partner will inform one of our trained community navigators who will connect with the interested participant to review the study information sheet and ask the participant to provide written consent to participate. Once the participant agrees to participate, the navigator will document the participant's contact information, and assist the participant in obtaining and understanding how to use and return their FIT via mail. The navigator will also give the participant a short survey (attached) to complete. The FIT test, instructions, survey, and mailing envelope will be contained in a "FIT Kit," a labeled plastic bag, that will be

dispensed to participant by the community navigator. The FIT and survey will be returned to the UICC via mail or dropped off at the barber or hair salon using a drop box (to be picked up regularly by research personnel), where it will be processed by key research personnel following the manufacturer's instructions. Participants who receive their FIT from the barber or hair salon will be offered a \$25 gift certificate to the barber or hair salon for use towards a future service. Each community navigator will keep a tally of the number of participants who are approached, eligible, and who decline to participate in screening for evaluation purposes. All potential participants will be informed that declining participation will not influence their ability to participate in any future activities at either business or with the UICC.

In addition to recruitment efforts in the barber shop and beauty salon, our community navigators who are trained on the study protocol will attend community events in the South Shore and surrounding communities such as the annual African Festival of The Arts (<https://www.aihua.org/african-festival-of-the-arts>) where UICC hosts an informational table each year. These navigators will use the attached CRC screening flyer, and engage with each potential participant to provide information and education about CRC screening using the attached script. If the participant is interested, the navigator will review the study information sheet and ask the participant to provide written consent to participate. Once the participant agrees to participate, the navigator will document the participant's contact information, and assist the participant in obtaining and understanding how to use and return their FIT. The navigator will also give the participant a short survey (attached) to complete. The FIT and survey will be returned to the UICC via mail or dropped off at the barber or hair salon using a drop box, where it will be processed following the manufacturer's instructions. Any positive FIT will be promptly reported (within 48 hours) to the MSHC clinical navigator, who will follow standard practices to register the participant as a patient, and navigate the participant through standard medical care if clinical follow-up is needed due to a positive screening and need for a diagnostic examination within the MSHC System. Participants who receive their FIT from a community navigator outside of the barber or hair salon setting will be offered a \$25 incentive (Walgreens store gift card or cash) to be paid upon receipt of the FIT to UICC. Each navigator will keep a tally of the number of participants who are approached, eligible, and who decline to participate in screening for evaluation purposes.

Standard of Care Comparison Group/Control Arm

For the standard of care control arm, we will obtain deidentified aggregate data from the Mile Square Englewood patients that are approached following standard practice utilizing clinic schedules, walk-ins, etc. to identify potentially eligible participants for CRC screening during the intervention period. This aggregate data will include the number approached, the number eligible, the number that take and return the FIT kit, and the number of FITs returned. Among those that return the FIT, aggregate data will be provided detailing the proportion of positive FITs, the proportion of positive FIT participants who return for diagnostic services, and the proportion of detected cancers.

Table 2. Subject Enrollment Plan

Screening Target	Community-Based (Intervention Arm)
Colorectal	
 Community navigators will work with local businesses (barber shop, hair salon) to identify and screen eligible community members within or near the South Shore community area. The navigator will engage with each potential participant using the attached script. If the participant is interested, the navigator will document the participant's contact information, and assist the participant in obtaining and returning their FIT. Community navigators will attend community events to post the informational flyer and provide education about CRC to community members. At these events, they will identify and screen eligible community members within or near the South Shore community area. The navigator will engage with each potential participant using the attached script. If the participant is interested, the navigator will document the participant's contact information, and assist the participant in obtaining and returning their FIT.
Screening Target	
 Standard of Care Clinic-Based Comparision Group (Control Arm)
Colorectal	
 These procedures are a detailed summary of the existing lay navigation program at MSHC. These procedures are unrelated to our research, except to demonstrate how the existing navigation program from which we will obtain deidentified data works. Lay clinic navigator use clinic schedules and walk-ins to identify and screen eligible participants within the Englewood MSHC. The navigator engages with each potential participant using standard scripted language. For interested patients, the navigator documents interest and FIT dispensing as appropriate, and assists the patient in obtaining and returning their FIT. Lay clinic navigators attend community events as normally scheduled to provide community-based health education and referral to the MSHC. At these events, they identify and screen eligible community members within the Englewood community area.

